8.1.1.4 Site(s) Performing Correlative Study

Pharmacokinetics

Samples will be processed at Stanford and then sent to Genzyme/Sanofi who will measure plasma levels of Plerixafor.

SDF-1

Samples will be processed at Stanford and picked up by a representative of lab at Stanford University

8.1.1.5 Coding of specimens for privacy protection

All PK and SDF-1 samples will be labeled the patient's study specific study number and initials.

Version #11, Date: 04-29-2015 Page 33 of 52

9. STUDY CALENDAR

	Day -7 (+/- 3)	Day 0 (+/-3)	Day 1	Day 4 b (+/-2)	Day 8 (+/- 3)	Day 15 (+/- 3)	Day 22 (+/- 3)	Day 29 (+/-3)	Day 35 (+/-7)	30 days post Plerixafor	MRI Eval (every 8- 12 wks per SOC)	6 months after start of XRT (+/- 2 wks)	Every 3 months after progress- ion
Continuous Plerixafor Infusion			X					a					
PICC Placement		X											
Informed Consent	X												
Demographics	X												
Medical History	X												
Con Meds		X											
Physical Exam	X		X		X	X	X a	Xa					
Vitals	X		X	X ^b	X	X	X a	Xa					
Height	X												
Weight	X												
KPS	X		X		X	X	X a	Xa					
CBC with diff	X		X	X ^b	X	X	X a	Xa					
Serum Chemistry	X		X	X ^b	X	X	X a	Xa					
Troponin			X			X		Xa					
Urinalysis	X												
Coag Panel (INR/PTT)	X												
SDF-1 ^b			X			X ^c		Xac					
PK ^b			X		X	X	X a	Xa					
ECG	X		X	X ^b	X	X	X a	Xa					
Adverse Events			У	ζ									
MRI									X		X	X	
Pregnancy Test	X												
TMZ (per SOC)									X				
Survival Status													X

- a. Not applicable for patients enrolled in the 200 $\mu g/kg/d$ x 2 wks (continuous infusion) dose level b. Phase I patients only c. At discontinuation of Plerixafor infusion (+/- 1 week)

10. MEASUREMENTS

For clinicaltrials.gov and Stanford Clinical Trials Directory compliance

Primary Outcome Measure Definition: Safety and tolerability of the continuous infusion of Plerixafor subsequent to irradiation.

Title: A Phase I/II study of local field irradiation and temozolomide followed by continuous infusion Plerixafor as an upfront therapy for newly diagnosed glioblastoma GBM.

Time Frame: Six month progression free survival from first day of radiation.

Safety Issue: Is this outcome measure assessing a safety issue? Yes

Note: Each outcome measure listed within the protocol will necessitate legally required results reporting to clinicaltrials.gov within one year after the completion of the primary outcome measure.

10.1 Primary and Secondary Outcome measures

Our primary objective in the Phase I component is to ascertain whether the highest dose is tolerated with acceptable side effects (400 micrograms per kilogram per day for four weeks). Our Primary objective in the Phase II component is to assess progression free survival at 6 months.

10.1.1 Relevant Subset

The first 9 patients will be treated accordingly to the dosing algorithm depicted in Table 12.1. The starting dose will be 200 micrograms per kilogram per day for four weeks. We will wait one week after the completion of the infusion at one dose level before proceeding. Once the final dose is determined at the Phase I portion of this study, then another 20 patients will be treated at the dose determined maximally tolerable.

10.1.2 Measurement Definition

• The primary outcome is dose-limiting toxicity, which is defined as the absence of cardiac arrhythmia or grade III or IV adverse events.

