2.4 Study Design

For clinicaltrials.gov and Stanford Clinical Trials Directory compliance

- State the primary purpose for the protocol:
 - o Treatment
- State the interventional model from these choices:
 - Single Group
- State the number of intervention arms.
 - o One
- State whether the study will be masked (at least one party is unaware of the treatment)
 - o **Open**: no masking is used
- State whether the study is randomized.
 - o No
- State type of primary outcome or outcome that the protocol is designed to evaluate:

Safety (Phase I) Efficacy (Phase II)

Phase I

The Phase I is designed to evaluate safety. A total of 9 newly diagnosed patients will be enrolled within four weeks of surgery (biopsy, partial resection or gross total resection). In order to minimize the chances for local angiogenic migration into the irradiated field, irradiation will be administered to the area encompassed by T2 FLAIR imaging plus a 2 cm margin to 46 Gy with a focal boost to the enhancing area to 60 Gy over a six-week period. Temozolomide 75 mg/M²/d starting the day of radiotherapy will be administered for 42 days concurrent with irradiation. Eight days prior to irradiation completion, patients will have a PICC line placed. Seven days prior to irradiation completion, the continuous infusion of Plerixafor will be initiated using a step-wise dose escalation based on the modified toxicity probability interval (mTPI) method. All treatments will start one week prior to completion of radiotherapy with concurrent temozolomide for patients with newly diagnosed glioblastoma. This dose escalation study begins with an intermediate dose of 200 µg/kg per day for four weeks. The first 3 patients will be enrolled at this starting dose. Enrollment within a dose level will be staggered so that there is at least 1 week between patients. If tolerability and safety is established after the 4 week treatment period, then the fourth patient will be enrolled at the higher target dose of 400 µg/kg per day for four weeks. We will wait one week after the last infusion at one dose level before proceeding to the next dosage level.

If a patient experiences a DLT, then s/he will be removed from study and the next patient treated at the lower dose level as dictated by the mTPI table.

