4. TREATMENT PLAN

4.0.1 Screening

The following procedures will be performed for all potential subjects at the Screening visit to be conducted 7 days prior to the start of Plerixafor infusion (+/- 3 days):

- Written informed consent must be obtained from the patient prior to performance of any study-specific tests or procedures
- Confirm Eligibility Criteria
- Post-operative, contrast-enhancing imaging
- Demographics: birth date, race/ethnicity and gender at birth
- Medical history
- Cancer history
- Physical Exam
- KPS
- Concomitant medications
- Vital Signs (including height and weight)
- ECG
- Laboratory tests: CBC with differential, Comprehensive Metabolic Panel (including: sodium, potassium, chloride, CO2, glucose, creatinine, urea nitrogen, calcium, protein, albumin, total bilirubin, ALK Phosphatase, AST, ALT and magnesium), Pregnancy Test (only for women of child bearing potential), INR, PTT, and Urinalysis with microscopic

Day 0 (within 3 days of beginning of Plerixafor infusion):

• Placement of the PICC line and infusion pump

Day 1 must occur 7 days (+/- 3 days) prior to the completion of XRT:

- Physical Exam
- KPS
- Vitals: pre-dose, 15 min (+/- 5 min), 30 min (+/- 5 min), 1 hr (+/- 15 min), 2 hrs (+/- 15 min) 3 hrs (+/- 30 min) and 6 hrs (+/-30 min) after the start of Plerixifor infusion
- Laboratory tests: CBC with differential, Complete Metabolic Panel (including: sodium, potassium, chloride, CO2, glucose, creatinine, urea nitrogen, calcium, protein, albumin, total bilirubin, ALK Phosphatase, AST, ALT and magnesium), Troponin
 - o Patients may proceed with the Plerixafor infusion even if the Day 1 ANC and platelets no longer meet inclusion criteria 3.1.7 due to the concurrent temodar and radiation and at the investigator's discretion; Thrombocytopenia should be ≤ grade 2
- Phase I only: SDF-1 levels (within 24 hours prior to the start of infusion)
- Phase I only: Samples for PK analysis will be drawn prior to and 1 hour (+/- 10 min) after start of the infusion of Plerixafor

Version #11, Date: 04-29-2015 Page 23 of 52

- ECGs: prior to the start of the Plerixafor infusion and 6 hours (+/- 30 min) after
- Phase I only: ECG 3 hours (+/- 30 min) after start of Plerixafor infusion
- Begin Plerixafor infusion in outpatient unit.
- Observe patients for 6 hours after the start of the Plerixafor infusion
- Patient will be discharged home after at least 6 hours with infusion pump.

Day 4 (+/- 2 days) for Phase I patients only

- Vitals

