4.2 Criteria for Removal from Study

The investigator has the right to discontinue a patient from study drug or withdraw a patient from the study at any time. In addition, patients have the right to voluntarily discontinue study drug or withdraw from the study at any time, for any reason. Reasons for discontinuation or withdrawal include, but are not limited to:

- Patient withdrawal of consent
- Progression of disease by RANO criteria, as determined by the investigator
- DLT (any AEs with suspected causal relationship with Plerixafor >= grade 3 including ECG changes indicative of ischemia, ventricular tachycardia)
- Investigator decision (eg, symptomatic/clinical deterioration or not in the patient's best interest to continue in the study)
- Patient is lost to follow up
- Death
- Non-compliance of the patient with protocol mandated procedures
- Any unacceptable toxicity

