6.1 Dose Limiting Toxicities

DLT is defined as any hematologic or non-hematologic AE grade ≥3 with a suspected causal relationship to Plerixafor (including including ECG changes indicative of ischemia, ventricular tachycardia).

- Patients will be monitored for DLTs for 5 weeks from the start of the Plerixafor infusion.
- DLT's in the first cohort may occur before or after 14 days. If a DLT occurs in weeks 3 or 4 of treatment, we will treat next patient with a dose of 200 μg/kg/d x2 weeks. If a DLT occurs from the start of treatment through the second week of treatment, we will

Version #11, Date: 04-29-2015 Page 27 of 52

treat next patients at a dose of 100 μ g/kg/d x 4 weeks. If a patient experiences a DLT, the infusion will be discontinued. The next patient treated at the lower dose level as dictated by the mTPI table. If an early dose limiting toxicity occurs at lowest dose level (200 μ g/kg/d x 2 wk or 100 μ g/kg x 4wks) then the protocol will be stopped at that point.

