7. ADVERSE EVENTS AND REPORTING PROCEDURES

7.1 Potential Adverse Events

Safety will be assessed by monitoring clinical and laboratory evaluations and AEs.

Definitions

Adverse Event

An AE is any untoward medical occurrence associated with the use of the investigational product (active or placebo drug, biologic, or device) in a clinical investigation patient, which does not necessarily have a causal relationship with the investigational product. An AE can, therefore, be any unfavorable and unintended symptom, sign, disease or condition, or test abnormality whether or not considered related to the investigational product.

AEs may include, but are not limited to:

Subjective or objective symptoms spontaneously offered by the patient and/or observed by the investigator or medical staff

Clinically significant laboratory abnormalities

A significant worsening of the patient's condition from study entry

Disease signs and symptoms and/or laboratory abnormalities existing prior to the use of the study treatment that resolve but then recur after treatment

Disease signs and symptoms and/or laboratory abnormalities existing prior to the use of the study treatment which increase in frequency, intensity, or a change in quality after treatment

Version #11, Date: 04-29-2015 Page 28 of 52

Since prior studies using this medication have included premature ventricular contractions (PVCs), there will be a temporary interruption of plerixafor treatment for abnormalities in serum magnesium, calcium, or potassium at a Grade 2 or more severe. The study medication may be resumed following correction of these electrolyte abnormalities as confirmed by repeat serum level testing. Supplementation to include magnesium sulfate, calcium carbonate, or potassium chloride may be used as clinically indicated.

Serious Adverse Events (SAEs)

A SAE is any adverse event that results in any of the following outcomes:

- Death
- A life-threatening experience
- Requires inpatient hospitalization or prolongs existing hospitalization
- A persistent or significant disability/incapacity
- A congenital anomaly/birth defect
- Important medical events that may jeopardize the patient and may require medical or surgical intervention to prevent 1 of the outcomes listed above

Hospitalizations that occur under the following circumstances are not considered to be SAEs:

- were planned before entry into the clinical study;

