12.1 Statistical Design

This is a dose-escalation study with three planned dose levels using the modified toxicity probability interval (mTPI). The mTPI method is a competitor to the usual 3+3 dose escalation scheme and to the Continuous Reevaluation Method (CRM), mTPI has the advantage of having been peer-reviewed in both the statistical literature and in the oncology literature [74]. The design has the further advantage of allowing the investigators to conduct the study without constant reference to a biostatistician (as required by the CRM approach). It also allows for planned de-escalation as in this protocol

Planned dose levels are 200 μ g/kg/d x 2 wks (continuous infusion), 100 μ g/kg/d x 4 wks, 200 μ g/kg/d x 4 wks, and 400 μ g/kg/d x 4 wks. The starting total dose will be the middle dose 200 μ g/kg/d x 4 wks.

If a DLT occurs from Day 15-28, we will treat next patient with a dose of 200 μ g/kg/d x 14 days. If a DLT occurs from day 0-14, we will treat next patients at a dose of 100 μ g/kg/d x 28 days. If a patient experiences a DLT, the infusion will be discontinued. The next patient treated at the lower dose level as dictated by the mTPI table. If an early dose limiting toxicity occurs at lowest dose level,200 μ g/kg/d x 2 wk or 100 μ g/kg x 4wks, then the protocol will be stopped at that point.

The design is based on a Bayesian calculation of the posterior probability of toxicity at each dose. The following settings have been used:

- * The target toxicity level. In this study we use the same level of 30% as in [74], which also corresponds informally to the target toxicity of the 3+3 design.
- * The precision for that target toxicity (here plus or minus 5 percentage points).
- * The maximum sample size across all dose (here 9).
- * Planned dose levels 200 μ g/kg/d x 2 wks (continuous infusion), 100 μ g/kg/d x 4 wks, 200 μ g/kg/d x 4 wks and 400 μ g/kg/d x 4 wks. The starting total dose will be the middle dose 200 μ g/kg/d x 4 wks.

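### Phase I has two DLT definitions, and after one DLT its text lowers the dose or stops the protocol where Table 12.1 stays or continues

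*Combined protocol and SAP*

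**What the plan says.** Doses are written as µg/kg/d × weeks.

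**DLT definition.** Section 10.1.2 gives the Phase I primary outcome: "The primary outcome is dose-limiting toxicity, which is defined as the absence of cardiac arrhythmia or grade III or IV adverse events". Section 6.1 reads "DLT is defined as any hematologic or non-hematologic AE grade ≥3 with a suspected causal relationship to Plerixafor". Section 4.2 agrees with 6.1: "any AEs with suspected causal relationship with Plerixafor >= grade 3 including ECG changes indicative of ischemia, ventricular tachycardia".

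**Next dose after a DLT.** Section 6.1 opens its timing rule with "DLT's in the first cohort may occur before or after 14 days". A DLT in weeks 3 or 4 sends the next patient to 200 × 2, and one in the first two weeks to 100 × 4. Section 12.1 repeats the rule without the first-cohort opening: "If a DLT occurs from Day 15-28, we will treat next patient with a dose of 200" for 14 days. Section 2.4 says a patient with a DLT is handled as follows: "then s/he will be removed from study and the next patient treated at the lower dose level as dictated by the mTPI table". Sections 10.1.1, 12.1 and 12.4.2 all name Table 12.1 as the dosing algorithm. Its row for one DLT reads D S S S S E E E E for 1 to 9 patients at that dose.

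**Stopping.** Sections 6.1 and 12.1 stop the protocol after an early DLT at 200 × 2 or 100 × 4. In the table key, D at 200 × 2 means treat the next patient at the same dose, and only U ends treatment there.

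**The concern.** The DLT count and the next-dose rule are the Phase I primary endpoint and its decision rule, and each exists in two incompatible forms.

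The wording of 10.1.2 as an absence is an evident slip, but correcting it does not align the definitions. The protocol itself expects events that separate them. Section 4.0.1 lets the infusion start "even if the Day 1 ANC and platelets no longer meet inclusion criteria 3.1.7 due to the concurrent temodar and radiation", with no ANC floor, and section 7.1 notes premature ventricular contractions in earlier studies. A grade 3 neutropenia attributed to temozolomide, or a grade 1–2 ventricular contraction, is a DLT under 10.1.2 but not under 6.1. One such event in three patients turns 0/3 (E) into 1/3 (S).

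On dosing, after one DLT in patient 2 or 3 a clinician following 6.1 lowers the dose and a statistician following Table 12.1 keeps it, each with support in the protocol. After an early DLT at one of the two lower levels, one rule ends the protocol and the other treats another patient. Phase II depends on the outcome either way: section 10.1.1 and the schema note carry forward the dose found in Phase I, while section 2.4 makes Phase II conditional on reaching 400 × 4 without significant toxicity.

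**Working it through.** **1. Reproduce Table 12.1.** Inputs from section 12.1: target 0.30 ± 0.05, Beta(1,1) prior, at most 9 patients. With x DLTs in n patients the posterior is Beta(1+x, 1+n−x). Divide the posterior mass in (0, 0.25), (0.25, 0.35) and (0.35, 1) by the interval length; the largest value gives E, S or D. D becomes U if P(rate > 0.30) > 0.95; this cutoff is assumed, since the documents do not state it. All 54 cells match, so the table follows from its stated settings and it is the text that departs from it.

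**2. The two rules side by side after one DLT.**

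| Situation | Text (6.1, 12.1) | Table 12.1 and key |
|---|---|---|
| 200 × 4, 1 in 1 | lower | D: lower (agree) |
| 200 × 4, 1 in 2–5 | lower | S: same dose |
| 200 × 4, 1 in 6–9 | lower | E: escalate |
| 200 × 2, early DLT, 1 in 1 | stop protocol | D: same dose |
| 100 × 4, early DLT, 1 in 1 | stop protocol | D: down to 200 × 2 |
| Either lower level, early DLT, 1 in 2–5 | stop protocol | S: same dose |

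**3. Starting dose, each outcome known before the next patient.** Let p be the DLT rate at 200 × 4 (30% is the protocol target; the other rates are assumed).

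- Conflict, first DLT in patient 2 or 3: p(1−p) + p(1−p)².
- Table reaches 400: 0/3, or one DLT in patient 2 or 3 followed by 1/6 = E, which is (1−p)³ + 2p(1−p)⁵. With no further DLT, patients 7–9 are treated at 400.
- Text reaches 400: only 0/3, which is (1−p)³. After any DLT in the first three, the steps back up use all nine patients. The value is the same if the rule covers only the first cohort.

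**4. Three starting patients dosed before any outcome is known.** The one-week stagger (2.4) and five-week DLT window (6.1) allow this. Conflict is exactly one DLT in three, 3p(1−p)². The table reaches 400 with (1−p)³ + 3p(1−p)⁵; the text value is unchanged.

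| p | Conflict (3) | Table reaches 400 (3) | Text reaches 400 | Conflict (4) | Table reaches 400 (4) |
|---|---|---|---|---|---|
| 0.10 | 0.171 | 0.847 | 0.729 | 0.243 | 0.906 |
| 0.20 | 0.288 | 0.643 | 0.512 | 0.384 | 0.709 |
| 0.30 | 0.357 | 0.444 | 0.343 | 0.441 | 0.494 |

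**5. Dose selected as MTD.** Exact enumeration of nine sequential patients, pool-adjacent-violators on observed rates, dose closest to 0.30. Section 12.1 states no tie rule; here ties below 0.30 go to the higher dose. Rates are assumed for 200 × 2, 100 × 4, 200 × 4 and 400 × 4.

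| P(400 selected) | Table | Text, first cohort only | Text, any DLT at 200 × 4 |
|---|---|---|---|
| 5/5/10/20% | 0.760 | 0.669 | 0.662 |
| 10/10/20/30% | 0.488 | 0.404 | 0.395 |
| 5/5/10/20%, all ties to lower dose | 0.508 | 0.478 | 0.470 |
| 10/10/20/30%, all ties to lower dose | 0.382 | 0.344 | 0.334 |

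**6. DLT definition.** The documents give no rate of unrelated events. With a 10% related rate and an assumed unrelated rate u, P(0/3) = (0.9(1−u))³ = 0.625, 0.531, 0.373 and 0.250 at u = 0.05, 0.10, 0.20 and 0.30, against 0.9³ = 0.729 when only related events count.

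**7. Early stop.** Given three patients at a lower level, a 10% DLT rate and a share f of DLTs that are early, P(stop) = 1 − (1 − 0.1f)³ = 0.073, 0.143 and 0.209 at f = 0.25, 0.50 and 0.75.

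**The case against.** The strongest reply is that the documents largely settle which rule governs. Three sections put the patients on Table 12.1, and 2.4, 6.1 and 12.1 each tie the lower dose to that table. On this reading the table decides whether to de-escalate and timing chooses the level. That is probably the intent, but the wording does not deliver it. The pointer presupposes a lower dose, and the table gives none at 1/2 to 1/5. The first-cohort opening in 6.1 does not help, because the conflict arises in the first cohort and 12.1 omits the limit.

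Other points narrow the size:

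- The rules agree at 1/1. A first DLT in the E cells at 200 × 4 is rare, because 0/3 escalates first. The figures in steps 3 and 4 use only DLTs among the first three patients.
- At a 5% DLT rate the conflict in step 3 is 9.3%.
- The 7–21% for early stopping is conditional on three patients at a lower level. Unconditionally, with 10% at every level, it is about 1–3% if the table otherwise governs and 3.8–7.8% if the text does. It reaches about 15% under the text at 10/10/20/30%.
- The stop may be a deliberate safety rule, but nothing marks it as an exception to the table.
- Section 6.1 is the natural operational definition, and section 7.1 counts possibly related events as related. Some neutropenias would therefore count under both definitions; low-grade arrhythmia and events judged unrelated would not.

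**Conclusion.** The concern holds, and the plan is wrong as written rather than short of detail. At DLT rates of 10–30% at the starting dose, the two dose rules conflict with probability 17–36% with sequential outcomes, or 24–44% if three patients are dosed before any outcome is known. The text lowers the chance of reaching 400 × 4 by 10 to 13 points in the sequential case and by 15 to 20 points in the other. The loss in selecting 400 as MTD is 8 to 10 points, or 3 to 5 if ties go to the lower dose. These sizes rest on assumed DLT rates and, for the MTD, on an assumed tie rule. The effect of the two DLT definitions depends on an unrelated-event rate that the documents do not give. The contradictions themselves rest on no assumption.

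Two smaller slips do not affect the grade. The U text names 100 × 4 as the next lowest dose, which skips 200 × 4 when coming from 400 × 4. The synopsis escalates at the second patient, against three patients first in 2.4 and the table key.

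**What to change.** - Replace the definition in 10.1.2 by a cross-reference to 6.1.
- State in 2.4, 6.1 and 12.1 that Table 12.1 alone decides whether the dose is lowered. DLT timing only chooses between 200 × 2 and 100 × 4 when the table gives D or U at 200 × 4.
- State one action for an early DLT at 200 × 2 or 100 × 4: keep the stop as an explicit safety exception to the table, or delete it.
- Minor: make the U text step from 400 × 4 to 200 × 4, and correct the synopsis to three patients before escalation.

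The cost is amendment wording in the synopsis, 2.4, 6.1, 10.1.2 and 12.1, with no extra patients and no new analysis code.

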10.1.3 Measurement Methods

ECG will be performed twice weekly basis during treatment, a baseline troponin at the initiation of the study, and physical examination weekly during treatment. Follow up will take place with physical examination and a clinic visit monthly after treatment.

